5.3. Computing Environment

All statistical analyses will be performed using validated SAS statistical software Version 9.4 (or later), unless otherwise noted.

5.4. Baseline Definitions

For spot urinary UOx:Cr ratio, baseline is defined as the mean of all spot urinary UOx:Cr ratio values collected prior to the first dose date/time of lumasiran. Baseline for all 24-hour urine parameters (i.e. 24-hour urinary oxalate corrected for BSA, etc) is defined as the median of all measurements collected prior to the first dose date/time of lumasiran. For all other PD parameters (i.e., plasma oxalate, etc.), baseline will use the mean of all measurements collected prior to the first dose date/time of lumasiran.

For other parameters, baseline is defined as the last non-missing value prior to the first dose date/time of lumasiran, unless otherwise specified. If multiple values are collected at a single visit (e.g. height, etc.), the mean of the values collected at the same visit will be used.

5.5. Missing Data

Patients who discontinue the study prior to Month 6 will be encouraged to remain on study and complete their remaining clinical visits (excluding PK assessments) through the visit at Month 6 and only safety follow-up visits afterwards. All data collected regardless of whether it was collected before or after treatment discontinuation will be used for analysis. However, it is possible that data will remain missing.

For safety analyses, no date will be assigned to any AEs with fully missing dates and only partially missing dates will be imputed. An AE will be considered treatment emergent unless it can be unequivocally determined (from the partial onset date and/or a partial or complete stop date) that the event occurred prior to the first dose of lumasiran.

For medications with partial start or stop dates: the first day/month will be imputed for start date, and the last day/month will be imputed for stop date. For medications with a completely missing start date, the medications will be considered as started prior to the first dose of study drug in this study; medications will be classified as prior or both prior and concomitant depending on the medication stop dates. If any medications have a completely missing stop date, then the medication will be assumed as ongoing.

For partial dates of renal stone events (start and stop dates): the first day/month will be imputed for start date, and the last day/month will be imputed for stop date. It is not expected that renal stone dates will be completely missing.

Due to blood sample volume limitations related to patient age/size, missing data in blood sample tests are expected. For blood test parameters where fewer than 4 patients have available baseline values, no summary statistics will be provided, only by-patient listing will be provided.

5.6. Visit Windows

For tabular and graphical summaries, all data will be tabulated and analyzed per the evaluation visit as recorded on the electronic case report forms (eCRF) even if the assessment is outside of window.

Unless otherwise specified, data collected at an unscheduled visit will be included in by-patient listings and/or spaghetti plot figures, but no assignment of the scheduled visit will be made for the purposes of summary tabulations. However, unscheduled study visits will be used in the calculation of baseline values if prior to first dosing and for any categorical shift tables (e.g. shift from baseline to worst post-baseline value).

5.7. Interim Analysis

A primary interim analysis is planned when the first 16 enrolled patients complete Month 6 assessment or discontinue treatment (if applicable). The number of patients for the primary interim analysis is chosen due to the enrollment pattern and the need for evaluation of benefit risk in this population for regulatory submissions. It should be noted that this will also provide information on twice the number of patients originally planned to be enrolled in this study. No multiplicity adjustment is necessary, since no formal study hypothesis is being tested for this study.

Further interim analyses may be conducted for lumasiran regulatory submission purposes and/or publication requests.

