Patients who discontinue from study drug during the 6-month treatment period (defined as the time the first dose of study drug is administered on Study Day 1 through completion of the Month 6 assessments) will be encouraged to remain on the study and complete assessments (including 24-hour urine collections, but excluding PK assessments) through Month 6 (see [Table 1](#)). They will also be asked to complete safety follow-up visits, once every 3 months, per the safety follow-up schedule (see [Table 3](#) or [Table 4](#)) for up to 12 months after the last dose of lumasiran, or until PD recovery (whichever is earlier).

Patients who discontinue study drug after Month 6 will be asked to return for their next scheduled visit to complete early termination (ET) assessments and complete safety follow-up visits, once every 3 months, per the safety follow-up schedule (see [Table 3](#) or [Table 4](#)) for up to 12 months after the last dose of lumasiran, or until PD recovery (whichever is earlier).

PD recovery is defined as urinary oxalate  $>70\%$  of baseline, and plasma glycolate  $<30\%$  above baseline or  $\leq$  the ULN (see Section [3.3.1](#)).

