4. PATIENT POPULATION

4.1. Patient Definitions

The populations (analysis sets) are defined as follows:

- Safety Analysis Set: All patients who received any amount of lumasiran during study.
- Efficacy Analysis Set: All patients who received any amount of lumasiran and have at least one valid spot urinary UOx:Cr ratio value at baseline and at least one valid spot urinary UOx:Cr ratio value from assessment(s) at Month 3 through Month 6.
- Primary Interim Efficacy Analysis Set: Among first 16 enrolled patients, all patients who received any amount of lumasiran and have at least one valid spot urinary UOx:Cr ratio value at baseline and at least one valid spot urinary UOx:Cr ratio value from assessment(s) at Month 3 through Month 6
- PK Analysis Set: All patients who received one full dose of lumasiran and have at least one postdose blood sample for PK parameters and have evaluable PK data.

The Safety Analysis Set will be used for safety analyses and sensitivity analysis of efficacy. The Efficacy Analysis Set will be used to evaluate efficacy endpoints. The PK Analysis Sets will be used to conduct PK analyses of plasma lumasiran concentrations.

The primary analysis period is defined as the time period from the date/time of the first lumasiran dose administration until either the date/time of lumasiran dose administration at Month 6 or the date of the Month 6 visit (Day 169) for patients who discontinued treatment prematurely. Primary analysis will be conducted using all data collected in the Primary Analysis Period. All data up to the dosing at the Month 6 visit will be included in the Primary Analysis Period.

The extension period starts after the date/time of lumasiran dose administration at Month 6 until the end of the study. Analysis of Extension Phase will focus on long-term efficacy of lumasiran.

Duration of Study is defined as the time period from on or after the first date/time of lumasiran dose until the end of the study. Analyses of Duration of Study will summarize secondary endpoints using data collected during the entire study period. These analyses focus on long-term efficacy and safety effects of lumasiran during both the primary analysis period and the extension period.

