5.8. Analysis for Primary Endpoint

As this study will be ongoing at the time of the primary analysis, there will be an interim database lock when the last patient completes all Month 6 visit assessments. All data available as of the date of data cut for the interim database lock will be included in the interim CSR corresponding to the primary analysis period.

After the study is completed (i.e. all patients complete the long-term extension period and/or required safety follow-up visit(s)), the database will be locked, and all data will be summarized in the final CSR.

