If the fit of the autoregressive (1) covariance structure matrix fails to converge, the primary estimate will be calculated as the LS mean of the primary outcome variable average across scheduled visits of Month 3 to Month 6 (based on available measures), according to analysis of covariance (ANCOVA) model with covariate of baseline spot urinary UOx:Cr ratio value (mmol/mmol). This LS mean will be presented along with corresponding SEMs, 95% CI and p-value from the model.

Descriptive statistics will also be generated at each scheduled visit. Mean (+/- SEM) figures of percent reduction will be plotted as well as individual spaghetti plots and listings. A table of the mean maximum percent reduction during the 6-months will also be generated.

Missing data on 24-hour urinary oxalate corrected for BSA are expected in the pediatric patients to be enrolled in this study. Existing correlation analysis based on PH1 patients older than 6 years old of 24-hour urinary oxalate corrected for BSA and spot urinary UOx:Cr ratio is included in Section 10.3.

Primary Interim Analysis

A similar analysis will be performed for the primary interim efficacy analysis set, i.e., among the first 16 enrolled patients, those who received any amount of lumasiran and have at least one

valid spot urinary UOx:Cr ratio value at baseline and at least one valid spot urinary UOx:Cr ratio value from assessment(s) from Month 3 through Month 6.

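### The SAP 5.7 interim trigger counts a child as finished on stopping treatment, so the 16-child interim can proceed while a late-enrolled discontinuer's Month 3 to 6 samples are still due

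*SAP*

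**What the plan says.** The trigger is in SAP 5.7: "A primary interim analysis is planned when the first 16 enrolled patients complete Month 6 assessment or discontinue treatment (if applicable". One reason given for this interim is "the need for evaluation of benefit risk in this population for regulatory submissions".

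SAP 4.1 defines who is analysed: "Primary Interim Efficacy Analysis Set: Among first 16 enrolled patients, all patients who received any amount of lumasiran and have at least one valid spot". The definition goes on to require that ratio at baseline, and at least one more from Month 3 through Month 6. SAP 7.1 gives the method: "A similar analysis will be performed for the primary interim efficacy analysis set", that is, the repeated-measures model averaged over Months 3 to 6.

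On children who stop drug before Month 6:

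- Protocol 4.3.1 says they "will be encouraged to remain on the study and complete assessments (including 24-hour urine collections, but excluding PK assessments) through Month 6".
- SAP 5.5 says they "will be encouraged to remain on study and complete their remaining clinical visits (excluding PK assessments) through the visit at Month 6", and then: "All data collected regardless of whether it was collected before or after treatment discontinuation will be used for analysis".
- SAP 4.1 ends the primary analysis period of premature discontinuers at the Month 6 visit (Day 169), not at the stop date.

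For the later full primary analysis, SAP 5.8 says "there will be an interim database lock when the last patient completes all Month 6 visit assessments". It offers no treatment-discontinuation alternative.

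**The concern.** Protocol 4.3.1 and SAP 4.1, 5.5 and 5.8 all look to Month 6 whether or not the child is still on drug. Only the SAP 5.7 trigger lets treatment discontinuation stand in for Month 6. If the child who completes the trigger does so by stopping drug, the interim may go ahead while samples the plan intends to use are still to come. Nothing in the SAP holds the analysis for them, and the interim set requires at least one of them.

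The possible loss is selective, because it can fall only on children who stopped. The study has no control arm, and each of 16 children carries 1/16 = 6.25% of a simple mean. An interim estimate offered for benefit-risk evaluation should follow the same rule on off-treatment data as the analysis it anticipates.

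**Working it through.** **The plan's own figure.** No power calculation lies behind 16. SAP 5.7 says only that it is twice the number first planned. The Amendment 1 summary of changes gives that number as 8, and 2 × 8 = 16, so the statement agrees.

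**Step 1: calendar.** Protocol Table 1 uses 28-day months, so Months 3, 4, 5 and 6 fall on Days 85, 113, 141 and 169, each ±14 days. Spot samples are taken within 7 days before dosing (SAP 7.1).

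**Step 2: when is a child lost completely?** The child must stop before giving a Month 3 sample, and the other 15 must already have qualified. If those 15 qualify by reaching Month 6, the child's first dose must follow that of the last of them by at least (Month 6 day of that child) − (Month 3 day of the discontinuer):

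- nominal: 169 − 85 = 84 days
- shortest, using the windows: 155 − 99 = 56 days
- longest, using the windows and the 7-day sampling allowance: 183 − (85 − 14 − 7) = 183 − 64 = 119 days

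The interim set is then 15 of 16. A discontinuer enrolled earlier keeps accruing samples while the others finish.

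**Step 3: when is a child lost in part?** If the last child to qualify stops just after the Month 3, 4 or 5 sample, 1, 2 or 3 of the 4 visits are in hand and the child stays in the set. Whether the missing visits would have differed depends on dosing. Protocol Table 1 schedules no dose between Month 3 and Month 6 for children of 10 kg or more. Such a child who received the Month 3 dose has missed nothing when the predose Month 6 sample is taken. The missing visits bear on the treatment effect only in children under 10 kg, who are dosed monthly, or in a child who did not receive the Month 3 dose.

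**Step 4: illustrative size of a complete loss.** Assume the other 15 average the mean of the Day 85, 113, 141 and 169 spot reductions in SAP Table 2: (60.9 + 60.0 + 63.9 + 70.2)/4 = 63.75%. Those patients were older (SAP 7.1 describes the data as from patients above 6 years), so this is an assumption. If the missing child would have averaged a reduction of r%, omission overstates the 16-child mean by 63.75 − (15 × 63.75 + r)/16 = (63.75 − r)/16.

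| r (%) | 16-child mean (%) | Overstatement (points) |
|---|---|---|
| 63.75 | 63.75 | 0 |
| 45 | 62.58 | 1.17 |
| 30 | 61.64 | 2.11 |
| 15 | 60.70 | 3.05 |
| 0 | 59.77 | 3.98 |

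The 30% row corresponds to the protocol's PD-recovery threshold, urinary oxalate above 70% of baseline.

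**Step 5: yardstick.** Standard deviations from Table 2 are SEM × √n: 6.7√13 = 24.2, 6.0√13 = 21.6, 6.6√13 = 23.8 and 4.0√11 = 13.3. The standard error of a 16-child mean is SD/√16, so between 13.3/4 = 3.3 and 24.2/4 = 6.0 points.

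**The case against.** The case against has real force.

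- **The chain of events is narrow.** Complete loss needs an early stop, a first dose well after the other 15, and a family that agrees to continue visits. Both documents only encourage continued follow-up, and SAP 5.5 accepts that data may stay missing. A reader might infer that the trigger removes children who stopped treatment as a class. The documents do not support that.
- **A trigger is not a data cut.** SAP 5.7 says when the analysis is planned, not which date closes the data. A later cut could recover some samples. This stands, but the SAP gives no cut date for this interim and no rule that it wait.
- **Stopping between Month 3 and Month 5 usually costs nothing in treatment terms.** A reader might infer that the values lost would show rebounding oxalate. For children of 10 kg or more who had the Month 3 dose, Protocol Table 1 rules that out as a difference from children who continue. The Amendment 2 rationale reported one child at 8.5 kg and the rest above 10 kg at that time.
- **The top of the range is unlikely.** An average reduction of 0% over Months 3 to 6 fits poorly with loading doses already given, quarterly maintenance at 10 kg or more, and follow-up of up to 12 months for PD recovery. A reader might also start from 70%, but that matches only the Day 169 spot value in Table 2.
- **The effect is visible and contained.** SAP 6.1 tabulates the interim set and lists discontinuers with reasons, and no formal hypothesis is tested. This helps a reader detect a 15-of-16 set but does not supply the missing values. Nor can the Safety Analysis Set sensitivity analysis use urines not yet collected.

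SAP 5.5 also speaks of discontinuing the study when it describes children who remain on it, so loose terminology may explain the trigger wording. That is a reason to correct the phrase.

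**Conclusion.** The inconsistency is real and the point holds in limited form. Under SAP 5.7 as written, the interim can proceed while a late-enrolled discontinuer's Month 3 to 6 samples are pending, contrary to the data rule in SAP 5.5 and the period definition in SAP 4.1. One child could be left out of the interim set, or a later stopper could contribute fewer visits.

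For one omitted child the overstatement is about 0 to 4 points on a reduction of about 64%. That is at most of the same order as the standard error and probably less. It rests on three assumptions: the Table 2 mean applies to this younger group, a simple mean approximates the model estimate, and the data cut follows the trigger closely. If suppression fully persists after stopping, the shift is zero.

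A reader might go on to doubt the study's primary result. The documents do not support that, because the SAP 5.8 lock waits for the last patient's Month 6 assessments.

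**What to change.** In SAP 5.7, replace the condition on the first 16 children with: *have completed the Month 6 assessments or stopped study participation before Month 6*. This agrees with SAP 4.1 and 5.5 and still lets the interim proceed when a child leaves the study altogether. It does not copy SAP 5.8, which has no clause for a child who leaves.

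The cost is one phrase and, compared with the present text, a possible wait until that child's Month 6 visit. The wait is no longer than if the child had stayed on treatment.

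If the cut has already been taken, state its date and list any discontinuers whose Month 3 to 6 samples were pending.

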5.8. Analysis for Primary Endpoint

As this study will be ongoing at the time of the primary analysis, there will be an interim database lock when the last patient completes all Month 6 visit assessments. All data available as of the date of data cut for the interim database lock will be included in the interim CSR corresponding to the primary analysis period.

After the study is completed (i.e. all patients complete the long-term extension period and/or required safety follow-up visit(s)), the database will be locked, and all data will be summarized in the final CSR.

6. STUDY ANALYSES

6.1. Patient Disposition

Number and percentage of patients will be tabulated for the following categories:

- Enrolled (signed informed consent and met eligibility)
- Safety Analysis Set
- Efficacy Analysis Set
- Primary Interim Efficacy Analysis Set
- PK Analysis Set

Summaries of the number and percentage of patients who discontinued treatment and/or withdrew from the study will be presented, along with the primary reasons for discontinuation of treatment and/or withdrawal from the study. Additionally, the number of patients who completed the Month 6 visit will also be displayed. A patient is defined as having completed the Month 6 visit if the patient has at least one spot urinary UOx:Cr ratio result for the Month 6 visit.

The number and percentage of patients enrolled by region will be summarized.

Data listings of those patients who withdrew and/or discontinued treatment including the associated reasons will also be presented.

The numbers of patients in each dose group will be summarized for the duration of study.

Disposition will be summarized throughout the study.

6.2. Demographics and Baseline characteristics

Descriptive statistics of demographic characteristics including but not limited to : age (months, 2 decimals), weight (kg), weight category (0-<10kg, 10-<20kg, \geq 20kg), gender, race, ethnicity, region, height (cm), and body mass index (BMI) will be presented. The modified z-score for all patients will be calculated and summarized for height, weight and body mass index (BMI) according to the Centers for Disease Control and Prevention (CDC) growth chart.[CDC National Center for Health Statistics 2019]

Additional baseline disease characteristics will be summarized using descriptive statistics. These include but are not limited to: spot urinary UOx:Cr ratio (mmol/mmol), plasma oxalate (umol/L), 24-hour oxalate excretion corrected for BSA (mmol/24hours/1.73m²), 24-hour urinary UOx:Cr ratio (mmol/mmol), eGFR (ml/min/1.73m²), spot urinary glycolate:creatinine ratio (mmol/mmol), plasma glycolate (umol/L), number of episodes with stone events in the past 12 months, and total number of patients reporting pyridoxine (vitamin B6) use prior to study entry. The collecting schedules are specified in the Schedules of Assessment in protocol.

6.3. Medical History

A complete medical and surgical history will be collected at the screening visit. The medical and surgical history will be coded using the Medical Dictionary for Regulatory Activities (MedDRA Version 21.1 or later).

Medical and surgical history will be summarized for the Safety Analysis Sets by system organ class, high level term and preferred term.

A tabular summary of historical PH1 disease characteristic information will be generated and include information on disease characteristics such as: time from diagnosis to first dose date (months), time from first symptoms to first dose date (months), time from first symptoms to diagnosis (months), number of siblings with PH1, reported history of disease events (e.g. pyelonephritis, renal stones, urinary tract infection). Reported medical history event rates may be adjusted based on age category, see Section 10.5.

Separate by-patient listings will be generated.

6.4. Prior and Concomitant Medications

Prior and concomitant medications will be coded using the World Health Organization (WHO) Drug Dictionary (September 2018 or later). Prior medications are defined as medications that were taken prior to the first dose of the study medication. Concomitant medications are defined as medications which were taken prior to and were ongoing while on lumasiran or medication(s) taken on or after the first dose date of lumasiran.

A tabular summary of the number and percentage of patients taking concomitant medications will be generated by anatomic therapeutic class (ATC) and preferred term. Data will be presented for the Safety Analysis Set.

By-patient listings will be generated separately for prior medications, concomitant medications and pyridoxine (vitamin B6).

Medications (Prior and Concomitant) will be summarized for the Safety Analysis Set.

7. STATISTICAL ANALYSIS

7.1. Primary Endpoint

The primary endpoint of this study is percent change in urinary oxalate excretion from baseline to the average of Month 3 to Month 6, which is measured by the primary outcome variable – percent change from baseline in spot urinary UOx:Cr ratio (mmol/mmol). The analysis will be conducted using the Efficacy Analysis Set.

Spot urinary UOx:Cr ratio is calculated from single-void urine collections. For all patients, triplicate single-void samples will be collected within 7 days prior to dosing, as specified in the Schedules of Assessment in the protocol. The mean value of these triplicate samples will be used as the baseline and postdose values in the analysis to account for the variability of the measure.

Despite historical data in healthy volunteers suggesting a natural decline in spot urinary UOx:Cr ratio in pediatrics, especially for children younger than 7 years old (Section 10.2.1), the effect of age on spot urinary UOx:Cr ratio in PH1 children is less clear (Section 10.2.2). Based on published data [Lieske 2005] at the time of writing of this SAP, it is considered that the potentially age-related decline in spot urinary UOx:Cr ratio level in children with PH1 is minimal, comparing with the anticipated treatment effect of lumasiran.

The primary analysis of the primary outcome variable will be performed using a restricted maximum likelihood (REML) based Mixed-effect Model Repeated Measures (MMRM) approach. Analysis will include fixed effects of scheduled visits and baseline spot urinary UOx:Cr ratio value (mmol/mmol), including patient as a random factor. An autoregressive (1) covariance structure will be used to model the within-patient error given the small sample size for this study. The primary estimate is the LS mean of the primary variable averaged over Month 3 to Month 6. This least square (LS) mean will be presented along with corresponding standard errors (SEMs), 95% confidence intervals (CI) and p-value from the model (i.e., testing against the null hypothesis of mean of primary outcome being equal to 0).

If the fit of the autoregressive (1) covariance structure matrix fails to converge, the primary estimate will be calculated as the LS mean of the primary outcome variable average across scheduled visits of Month 3 to Month 6 (based on available measures), according to analysis of covariance (ANCOVA) model with covariate of baseline spot urinary UOx:Cr ratio value (mmol/mmol). This LS mean will be presented along with corresponding SEMs, 95% CI and p-value from the model.

Descriptive statistics will also be generated at each scheduled visit. Mean (+/- SEM) figures of percent reduction will be plotted as well as individual spaghetti plots and listings. A table of the mean maximum percent reduction during the 6-months will also be generated.

Missing data on 24-hour urinary oxalate corrected for BSA are expected in the pediatric patients to be enrolled in this study. Existing correlation analysis based on PH1 patients older than 6 years old of 24-hour urinary oxalate corrected for BSA and spot urinary UOx:Cr ratio is included in Section 10.3.

Primary Interim Analysis

A similar analysis will be performed for the primary interim efficacy analysis set, i.e., among the first 16 enrolled patients, those who received any amount of lumasiran and have at least one

valid spot urinary UOx:Cr ratio value at baseline and at least one valid spot urinary UOx:Cr ratio value from assessment(s) from Month 3 through Month 6.

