7.3. Secondary Endpoints

For efficacy secondary endpoints, the Efficacy Analysis Set will be used; for PK secondary endpoints, the PK Analysis Set will be used.

Secondary endpoints in this study are as follows:

Extension Period (Month 6 to End of Study)

Percent change in spot urinary UOx:Cr ratio from baseline for all post-Month 6 visits will be summarized descriptively using the Efficacy Analysis Set. The analyses for 24-hour urinary oxalate corrected for BSA and 24-hour urinary UOx:Cr ratio will be carried out using Extension Period data as well.

Duration of Study (Baseline to End of Study)

Absolute changes in spot urinary UOx:Cr ratio and percent and absolute change in plasma oxalate from baseline using Efficacy Analysis Set will be performed similarly to primary analysis. In addition, percent and absolute change in plasma oxalate from baseline will also be analyzed using only patients in the Efficacy Analysis Set whose baseline plasma oxalate $\geq 1.5^*LLOQ$. LS means by postdose visits with corresponding SEM and 95% CIs will be displayed for the primary analysis period.

For continuous endpoints (including eGFR), descriptive statistics will be generated at each scheduled visit. Mean (+/- SEM) figures of actual values and changes from baseline will be plotted as well as individual spaghetti plots and listings. For binary endpoints, the number and associated percent of patients who met each threshold (e.g. $\leq ULN$ or $\leq 1.5 \times ULN$) at visits will be presented.

To demonstrate durability of the effect of lumasiran, for binary endpoints, (e.g. proportion of patients with spot urinary UOx:Cr ratio level $\leq ULN$ or $\leq 1.5 \times ULN$), tabular summaries of the number and percent of patients who met the threshold at post-baseline visits will be presented.

An analysis of the percentage of time that spot urinary UOx:Cr ratio is at or below the near-normalization threshold for the duration of study will be summarized. A patient is considered to have met the threshold if the spot urinary UOx:Cr ratio is $\leq 1.5 \times ULN$ at a post-baseline visit.

For each patient, the percentage of time that spot urinary UOx:Cr ratio is at or below the near-normalization threshold of $\leq 1.5 \times ULN$ will be calculated as follows:

$$\frac{\text{cumulative time at or below near normalization threshold}}{\text{cumulative time of valid assessments}} \times 100$$

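### SAP 7.3: by-visit LS-mean intervals for absolute change in spot ratio and for plasma oxalate leave out baseline sampling variation, so they are too narrow for a population mean

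*SAP*

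**What the plan says.** The study is single-arm (SAP 2.1), so the reported quantity is the LS mean itself and not a difference between arms. SAP 7.1 specifies REML with AR(1) errors and states "Analysis will include fixed effects of scheduled visits and baseline spot urinary UOx:Cr ratio value (mmol/mmol), including patient as a random factor". The SE, 95% CI and p-value come from that model, the p-value "testing against the null hypothesis of mean of primary outcome being equal to 0". If the model does not converge, the estimate is obtained "according to analysis of covariance (ANCOVA) model with covariate of baseline spot urinary UOx:Cr ratio value (mmol/mmol"). For the first 16 patients, "A similar analysis will be performed for the primary interim efficacy analysis set".

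SAP 7.3 carries the method to absolute change in the spot ratio and to plasma oxalate: "percent and absolute change in plasma oxalate from baseline using Efficacy Analysis Set will be performed similarly to primary analysis". The output is specified: "LS means by postdose visits with corresponding SEM and 95% CIs will be displayed for the primary analysis period". Plasma oxalate change "will also be analyzed using only patients in the Efficacy Analysis Set whose baseline plasma oxalate" is at least 1.5 times the LLOQ. SAP 5.2 assigns the LLOQ to any result below it, and SAP 8 gives that limit as 5.55 µmol/L.

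Unadjusted summaries are also planned. SAP 5.2 lists n, mean, SD and SE for continuous data. SAP 7.3 plans descriptive statistics at each scheduled visit for continuous secondary endpoints, and SAP 7.1 does the same for the primary: "Descriptive statistics will also be generated at each scheduled visit".

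The SAP does not say at which baseline value an LS mean is evaluated, which baseline is the covariate for plasma oxalate, or whether an interval refers to the enrolled baselines or to a wider population.

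**The concern.** In a two-arm trial, the uncertainty in the mean baseline largely cancels from the treatment contrast. Here there is nothing for it to cancel against. A model SE evaluated at the sample-mean baseline counts only the scatter around the regression line. It omits the fact that another sample of 20 children would have a different mean baseline and hence a different mean change.

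How much that matters depends on how strongly the outcome follows baseline. Percent change need not follow it much. Absolute change does almost by construction if the effect is roughly proportional. Plasma oxalate has a further link: a patient below LLOQ after treatment has an absolute change of exactly 5.55 minus baseline.

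SAP 5.7 says that no formal hypothesis is tested, so the interval is the main statement of precision. A reader who takes the secondary intervals as the precision for young children with PH1 in general would be misled. The tables would also show two different SEs for what is, with complete data, the same mean, without explanation.

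**Working it through.** The documents state no SE, interval width or R² for these analyses, so there is no planned figure to reproduce.

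**Inputs from the documents.** n = 20 (SAP 5.1); the model (SAP 7.1) and its reuse (SAP 7.3); LLOQ 5.55 µmol/L and substitution at LLOQ (SAP 8, SAP 5.2). SAP Table 2 gives mean spot reductions of 60.9, 60.0, 63.9 and 70.2% at Days 85 to 169, in patients from an earlier study. The SEMs imply SDs of 6.7×√13 = 24.2, 6.0×√13 = 21.6, 6.6×√13 = 23.8 and 4.0×√11 = 13.3 points.

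**Assumptions.** The LS mean is taken at the sample-mean baseline, and each endpoint's own baseline is its covariate.

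**1. Algebra, complete data.** The LS mean at the mean baseline equals the raw mean. Its model variance is Var(y|x)/n, while its sampling variance is Var(y)/n. Hence

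model SE / true SE = √(1−R²), and coverage = 2·T₁₈(√(1−R²) × 2.101) − 1 at n = 20.

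| R² | SE ratio | Coverage |
|---|---|---|
| 0.05 | 0.975 | 94.5% |
| 0.25 | 0.866 | 91.4% |
| 0.50 | 0.707 | 84.5% |
| 0.80 | 0.447 | 64.0% |

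**2. Absolute change in spot ratio.** If change = baseline × fractional change, with the two independent, then R² = m²CV² / [m²CV² + SD²(1+CV²)]. With m = 0.65, baseline CV = 0.5 and SD = 0.20: 0.1056 / (0.1056 + 0.0500) = 0.68, SE ratio 0.57, coverage 75%. Over CV 0.3–0.9 and SD 0.10–0.24, R² runs from 0.38 to 0.95 and coverage from 89% to 36%.

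A simulation added triplicate voids (void CV 0.2–0.4), with mean reduction 61%, SD 15–25 points and baseline CV 0.3–0.7, and fitted ANCOVA at a single visit. R² was 0.41–0.84. Coverage ran from 86.5% down to 53.6%, against 94.8% to 91.1% for a one-sample t interval. Gamma-distributed void noise moved the ends of the model-interval range by less than one point. Fitting the REML model itself to two of these scenarios (t with 18 df assumed; 668 and 653 runs) gave 80.8% against 94.6%, and 71.5% against 93.0%.

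**3. Plasma oxalate.** A patient below LLOQ at a visit contributes 5.55 − baseline. For baselines of 9 and 15 that is −3.45 and −9.45, both exactly on a line in baseline. Assumed: baseline median 8–18 µmol/L, log-SD 0.5, mean reduction 30–50%, so that 9–73% of values sit at LLOQ. ANCOVA at a single visit, with n = 20 overall and n = 10 assumed for the subset (baseline ≥ 1.5 × 5.55 = 8.3 µmol/L), gave:

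| Endpoint | Model interval | One-sample t |
|---|---|---|
| Absolute change | 83.9% to 48.4% | 92.8–93.8% |
| Percent change | 94.7% to 77.1% | 94.6–95.0% |
| Subset, absolute | 87.3% to 67.5% | 91.8–94.7% |
| Subset, percent | 94.5% to 90.2% | 93.9–95.1% |

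A smaller run of the repeated-measures model (6 visits, 250 runs per scenario, assumed gradual onset) gave about 70–86% for absolute change, generally a few points above ANCOVA on comparable data (68–82%), and about 88–97% for percent change.

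**4. Primary percent change.** If percent reduction does not depend on baseline, the only link is baseline as denominator. Under the spot-ratio assumptions with SD 20 points, averaged over Months 3–6, this gives R² 0.001–0.05 and coverage 93.8–94.9%, against 94.3–95.0% for the t interval.

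**The case against.** The strongest reply is that nothing here is invalid. An LS-mean interval conditional on the observed covariates is the ordinary meaning of the output, the protocol calls the analyses mainly descriptive (7.2), and the SAP never claims a population interval. That stands, and it is why the fault lies in how the interval will be read and not in the model.

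A second reply is that the missing information is nearly all planned: by-visit means and SEs in SAP 5.2 and 7.3 do include baseline variation. That also stands, and it makes the fix cheap. But the only intervals SAP 7.3 describes for these change endpoints are the LS-mean ones. The general promise of 95% CIs in SAP 5.2 refers onward to the later sections, so it does not settle the matter.

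Third, the sizes rest on assumed CVs, SDs and plasma oxalate levels. True. The direction does not depend on them, but the figures do. SAP 5.5 expects missing blood samples, so n = 20 is optimistic for plasma oxalate.

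Two stronger readings are tempting and should not be drawn. One is that the primary interval, its ANCOVA fallback and the 16-patient interim are compromised. Step 4 shows a loss of no more than about one point. A larger loss needs percent reduction to depend on baseline: an assumed floor on the ratio, giving R² 0.14–0.26, would lower coverage to about 90–93%. The documents describe no such floor. The other is that a visit with every patient at LLOQ would have zero fitted variance and a collapsed interval. The planned model has one variance structure common to all visits, so that does not follow.

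**Conclusion.** The point holds for the SAP 7.3 endpoints and is minor. As intervals for a population mean, the by-visit LS-mean CIs are clearly too narrow for absolute change in spot ratio and absolute change in plasma oxalate. For percent change in plasma oxalate they range from adequate to clearly too narrow, depending on how many values lie at LLOQ. The restriction to baseline ≥ 1.5 × LLOQ eases this but uses the same kind of SE.

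The conclusion assumes LS means taken at the sample-mean baseline with the endpoint's own baseline as covariate. The coverage ranges are ANCOVA results under assumed inputs. The planned repeated-measures model may be somewhat less affected for plasma oxalate. With complete data the point estimates do not change. No test or decision rule depends on these intervals, and SAP 7.1 needs no change.

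**What to change.** Keep the models and point estimates. In SAP 7.3:

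- At each visit, beside the LS-mean CI, report an unadjusted one-sample t 95% CI, that is, mean ± t(n−1) × SE from the descriptive statistics already planned. Do this for absolute change in spot ratio and for percent and absolute change in plasma oxalate, including the restricted subset.
- Give the number of plasma oxalate values at LLOQ at each visit.
- Label the LS-mean CI as conditional on the observed baselines.
- Record the addition in SAP Section 8.

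The cost is one column per table and a sentence of text. The added intervals will be wider, about 1.3 to 2.7 times for absolute change in spot ratio under the assumptions above. They are not perfect either: because the data are skewed, they cover about 91–95% for that endpoint. Where visits are missing, the unadjusted mean will differ slightly from the LS mean, which a footnote can explain.
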